Research Protocol

Title: Does Use of a Facemask Reduce the Risk of Aerosolization During Anesthesia Assisted Upper Endoscopic Procedures: A Randomized Controlled Pilot Trial

PI: [name] [name]

Co-Investigators: [name] MD, [name], MS, [name], MD, MS, [name], MS, [name], [name], [name], [name], [name], [name], [name].

Introduction

There is little evidence describing the aerosolization of potentially infectious particles during gastrointestinal endoscopy. Such a phenomenon could potentially place medical staff and patients alike at exposure risk despite the use of personal protective equipment as once aerosolized, microscopic water droplets could remain suspended in the air for hours and represent a potential risk of spread of infectious agents. We propose a randomized controlled pilot trial to assess aerosolization and the potential use of an endoscopic patient facemask to reduce the risk of viral transmission.

Background and Significance

Unfortunately there is a lack of data regarding infectious risk posed to healthcare providers by aerosolization during upper endoscopy. Furthermore, the current COVID-19 pandemic has heightened stress surrounding the danger of potential aerosolizing procedures. While personal protective equipment may reduce some risk, aerosolized particles can remain suspended in the procedural room environment and may lead to transmission despite the use of personal protective equipment. There is only one prospective observational study assessing aerosolization during endoscopy, which used a handheld particle detector in 93 patients undergoing upper endoscopy and found significant increases in particle suspension within the air in the endoscopy procedure room at a distance from the subject where the endoscopist and support staff would be located.

Given the current lack of evidence on particle aerosolization during endoscopy, we plan to conduct a randomized controlled trial utilizing a commercially available particle detector to assess particle suspension in the air during upper endoscopic procedures. We hypothesize that use of an endoscopic patient facemask reduces periprocedural aerosolization during upper endoscopic procedures. Our initial effort will be focused on conducting a pilot trial to assess population variability as no baseline data exists for aerosolization in the general population. We hope to subsequently conduct a larger scale trial to fully test our hypothesis. If an endoscopic facemask significantly reduces aerosolization it could be used to decrease infectious risk to providers while posing minimal risk to the patient and without significantly altering the endoscopic procedure.

Methods

Study Design: Prospective randomized controlled trial

Sample Population

- All patients presenting for an elective upper endoscopic procedure with monitored anesthesia care
- For the pilot trial we plan to recruit 50 total patients, 25 patients in the control arm without a procedural facemask and receiving 2-4 L/min of oxygen via nasal cannula and 25 with a specially designed facemask. An additional 10 patients will be enrolled to account for subject dropout as necessary. Sample size calculation was conducted for the purpose of estimating population variability with a 0.05 level of significance and 0.8 power level. This was done with the assistance of the Department of Quantitative Health Sciences at the Cleveland Clinic
- Inclusion Criteria:
 - All patients undergoing elective upper endoscopic procedures (upper endoscopy, ERCP, endoscopic ultrasound) with monitored anesthesia care at main campus Cleveland Clinic Q3 inpatient endoscopy unit.
- Exclusion Criteria:
 - Any patient requiring endotracheal intubation
 - Pregnant patients
 - Emergency procedures
 - Patients who require use of a facemask before or during the procedure due to medical necessity
 - Patients under the age of 18
 - Non-English speaking individuals
 - Patients unable to provide consent.
 - Any procedure done outside the designated procedure room.
 - If in the opinion of the anesthesiologist, a subject who was randomized to the control arm requires placement of the procedural mask to augment oxygenation, the subject will be removed from the study

Research Procedure:

- All patients undergoing an upper endoscopic procedure in the designated procedure room with monitored anesthesia care will be eligible for recruitment into the study once exclusion criteria are applied
- Patients will be randomized to receive an endoscopic procedural facemask or to undergo endoscopy without one at the time of enrollment in the pre-procedure holding area. Control subjects will receive supplemental oxygen (2-4 L/min) via nasal cannula as per our standard protocol. Use of this mask will not affect the risk of the procedure nor change the nature of the patient's endoscopy in any way. An example of this commercially available facemask is pictured below. The mask is currently used in the inpatient endoscopy unit at the main campus of the Cleveland Clinic is selected patients for oxygen delivery.

- In order to collect particle aerosolization data, use of a Met One GT-526S Handheld Particle Counter will be used. This device can detect particles of six different sizes ($0.3\mu\text{m}$, $0.5\mu\text{m}$, $1\mu\text{m}$, $2\mu\text{m}$, $5\mu\text{m}$ and $10\mu\text{m}$). This data can be directly downloaded from the device using the associated Comet software. Device pictured below:

- Endoscopy will be performed in accordance with standard procedures at the Main Campus Cleveland Clinic by either a staff gastroenterologist or a gastroenterology fellow trainee under direct supervision by a staff gastroenterologist.

- The device will be placed in a standardized position 12 inches from the head of the subject on a tripod. The device location will not hinder access to the subject by anesthesia, nursing or gastroenterology staff.

Data Collection:

- Data collected before the patient enters the procedure room:
 - Patient Demographics (age, gender)
 - BMI
 - Upper Endoscopic Procedure Type (ex: esophagogastroduodenoscopy, endoscopic ultrasound, endoscopic retrograde cholangiopancreatography)
 - Patient Mallampati Score
- Data collected in the procedure room prior to start of endoscopy:
 - Patient vitals including BMI and oxygen saturation
 - Patient positioning (left lateral decubitus, supine, prone).
 - Oxygen flow rate being administered by anesthesia staff
 - Number of individuals in the room
 - Peak and mean aerosolized particle counts for 5 minutes prior to endoscopy start
- Data collected during the procedure
 - Any change in supplemental oxygen requirement
 - Any intra-procedural manipulation of the patient's head and neck (ie. head tilt, jaw thrust)
 - Any removal and reinsertion of the endoscope
 - Any opening of the designated procedure room door
 - Any use of the endoscope working channel
 - Peak and mean aerosolized particle counts. This will be obtained during three intervals for six different sizes (0.3 μ m, 0.5 μ m, 1 μ m, 2 μ m, 5 μ m and 10 μ m). The three intervals are: A. A 5-minute baseline period before initiation of sedation. B. Intra-procedurally and C. Post procedurally for 5 minutes, which is defined as beginning after the endoscope is removed.
- Data collected post-procedurally
 - Total procedure duration
 - Total dosage of medications utilized for sedation
 - Use of any reversal agents
 - Peak and mean aerosolized particle counts for 5 minutes after endoscopy completed
- After the patient exits the procedure room no further patient data will be collected
- Post-procedurally patients will follow standard post endoscopy monitoring prior to discharge.

Sample Size Calculation and Data Analysis

Sample size calculation was conducted for the purpose of estimating population variability with a 0.05 level of significance and 0.8 power level. This was done with the assistance of the Department of Quantitative Health Sciences at the Cleveland Clinic.

Data will be described using means (standard deviations) for normally distributed continuous variables, medians [quartiles] for non-normally distributed continuous variables, and frequency (percentage) for categorical variables. Shapiro-Wilks test will be conducted for continuous variables to assess normality. Analysis of variance (ANOVA) or the non-parametric Kruskal-Wallis tests will be used to assess differences in continuous variables. The chi-square test and Fisher's exact test will be used to compare categorical variables as appropriate. A linear mixed model will be used to assess the association between the clinical factors and concentration level of each particle. The mixed model will be used to account for

within subject correlation. All tests will be two-tailed and performed at a significance level of 0.05.

Analyses will be performed using R software

Particle concentrations for the six sizes measured by the device (0.3 μ m, 0.5 μ m, 1 μ m, 2 μ m, 5 μ m and 10 μ m) will be assessed during three intervals: (1) 5 minute baseline prior to the procedure (2) during the procedure and (3) 5 minutes after endoscope removal. The primary endpoint for the study will be the mean / median concentration of each particle for the three measurement intervals. Our hypothesis is that use of the facemask will significantly decrease aerosolization of all particle sizes during the procedure when compared to controls.

Demographic, procedural and particle concentration data will be placed into a RedCap database, by Drs. [name] and [name]. Additional access to the database will be granted to [name], MS from the department of Quantitative Health Sciences who will be conducting the statistical analysis.

Adverse Events and Data Monitoring Committee (DMC)

This is a minimal risk study. The PI has been involved in procedures which utilized this device without any adverse events. Literature review as well as review of the MAUDE database failed to reveal any instances of complications stemming from the use of this facemask.

Consent

Consent will be obtained by one of the investigators in the pre-procedure area of the endoscopy suite. Patients will be given the option clearly to not participate in the research study while still participating in their planned endoscopic procedure. Subjects deemed not able to consent for the procedure themselves will not be included within the research study. Attached is the proposed consent document.

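### Removing control subjects who come to need the mask, after randomization and from one arm only, puts the between-arm comparison at risk of bias that the 10 spare patients cannot correct

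*Combined protocol and SAP*

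**What the plan says.** Under Research Procedure, allocation takes place "at the time of enrollment in the pre-procedure holding area", before any need that arises during the procedure can be seen.

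The exclusion list under Methods, Sample Population ends with a rule that depends on the anesthesiologist's opinion and gives no threshold: "randomized to the control arm requires placement of the procedural mask to augment oxygenation, the subject will be removed from the study". It is listed as an eligibility criterion but operates after allocation and names only the control arm.

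Two other exclusions name no arm: "Patients who require use of a facemask before or during the procedure due to medical necessity" and "Any patient requiring endotracheal intubation".

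The only provision for losses is this: "An additional 10 patients will be enrolled to account for subject dropout as necessary".

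Sample Size Calculation and Data Analysis states a between-arm hypothesis, "Our hypothesis is that use of the facemask will significantly decrease aerosolization of all particle sizes during the procedure when compared to controls", and plans two-sided tests at 0.05. It defines no analysis set. It does not say what happens to particle data already collected from a removed subject, and it plans no sensitivity analysis.

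**The concern.** Randomization makes the arms comparable only if everyone randomized stays in the comparison, or if losses work alike in both arms. Here they do not. Controls with an oxygenation problem leave; mask-arm subjects with the same problem remain, because the need cannot show itself in someone already wearing the mask.

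The arm-neutral criteria do not mend this. Facemask need during the procedure has the same blind spot in the mask arm. Intubation, if applied during the procedure, could remove subjects from either arm, but it is a different event.

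Whether bias follows depends on whether the removed controls would have aerosolized more or less than the others. Data Collection records "Any change in supplemental oxygen requirement" and head and neck manipulation during the procedure. That such events relate to particle counts is an inference, not something the documents state. At stake are the estimated mask effect, its test and, to a lesser degree, the control-arm variability estimate for the larger trial. If measurement stops when a subject is removed, no analysis can recover the lost data.

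**Working it through.** **The plan's own figure.** The 25 per arm cannot be reproduced, because no effect size, SD or precision target is given. Solving backwards at two-sided 0.05 and 80% power, the normal approximation gives (1.960 + 0.842) × √(2/25) = 0.79 SD, and the t-test gives 0.81 SD (0.809). I use 0.809 SD as the illustrative true effect; it is not in the documents.

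**Inputs.** From the documents: 25 per arm, 10 spare places, two-sided 0.05. Assumed:
- the spare places split evenly, so up to 30 are randomized per arm;
- 3 of 28 or 5 of 30 controls are removed, each leaving 25;
- a latent-normal correlation r between need for the mask and log concentration, 0.3 to 0.7 in size, of either sign. As a point-biserial correlation this is 0.18 to 0.42 at 3/28 and 0.20 to 0.47 at 5/30.

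**Shift of the retained-control mean.** With p the proportion removed and z = Φ⁻¹(1 − p), the shift is r × φ(z)/(1 − p).
- p = 3/28: z = 1.242, φ(z) = 0.1845, ratio 0.1845/0.8929 = 0.207. Shift for r = 0.3, 0.5, 0.7: 0.062, 0.103, 0.145 SD.
- p = 5/30: z = 0.967, φ(z) = 0.2499, ratio 0.2499/0.8333 = 0.300. Shift: 0.090, 0.150, 0.210 SD.

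Positive r (removed controls aerosolize more) lowers the control mean and makes the mask look less effective. Negative r does the reverse.

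**Rejection rate with no mask effect** (simulated t-tests, 100,000 trials for each setting):

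| Size of r | 3/28 | 5/30 |
|---|---|---|
| 0.3 | 5.6% | 6.1% |
| 0.5 | 6.4% | 8.5% |
| 0.7 | 8.1% | 11.9% |

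Analysis by assigned arm stays at 4.8% to 5.1% throughout.

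**True effect of 0.809 SD: estimate (power).** The assigned-arm columns assume that crossed-over controls are masked throughout.

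| r | Removal, 3/28 | Removal, 5/30 | Assigned arm, 3/28 | Assigned arm, 5/30 |
|---|---|---|---|---|
| 0.7 | 0.66 (0.69) | 0.60 (0.62) | 0.72 (0.79) | 0.67 (0.77) |
| 0.3 | 0.75 (0.76) | 0.72 (0.75) | 0.72 (0.76) | 0.67 (0.74) |
| 0 | 0.81 (0.82) | 0.81 (0.83) | 0.72 (0.74) | 0.67 (0.71) |
| −0.3 | 0.87 (0.88) | 0.90 (0.91) | 0.72 (0.72) | 0.67 (0.68) |
| −0.7 | 0.95 (0.94) | 1.02 (0.97) | 0.72 (0.70) | 0.67 (0.65) |

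The assigned-arm dilution is p × 0.809: 0.087 SD at 3/28 and 0.135 SD at 5/30.

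**Does extra enrolment help?** In a simpler model a fraction q of subjects needs the mask and has a mean higher by δ, so the bias is q × δ. With q = 20% and δ = 1 SD (both assumed), the bias is 0.20 SD at 25, 30 and 100 per arm. The rejection rate with no mask effect rises from 10.2% to 11.3% to 27.2%. Replacement controls pass through the same filter.

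**Control-arm variability.** The retained SD is 0.986 to 0.924 of its true value at 3/28 and 0.983 to 0.902 at 5/30, a fall of about 1% to 10%. The 95% confidence interval for an SD at n = 25 runs from 0.78 to 1.39 times the estimate, so this effect is small beside it.

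**The case against.** *It is a pilot.* Its stated aim and sample size concern variability, where the effect is minor. This lowers the weight of the point, but the plan still states a directional between-arm hypothesis and tests at 0.05.

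*The size is assumed.* It is. Removing 5 of 30 would use every spare control place on this one rule. The standard error of a difference at 25 per arm is √(2/25) = 0.28 SD, so the whole 0.06 to 0.21 SD range lies below one standard error.

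*The two-sided rejection rates hide direction.* This is correct. If removed controls aerosolize more, nearly all the excess rejections favour no mask, and false claims of benefit fall from 2.5% to between 0.2% and 1.4%. If they aerosolize less, false claims of benefit rise to between 4.1% and 11.9%. Which applies is unknown.

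*Covariates could help.* The plan collects baseline particle counts, BMI, Mallampati score and oxygen saturation, and plans a mixed model on clinical factors. Adjustment might reduce the selection but cannot be relied on to remove it. The plan does not say that the model includes arm.

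*Assigned-arm analysis answers another question.* It estimates the effect of assignment, and its dilution is similar in size to the bias. That stands as a real cost and is the reason for reporting a second analysis. In return, the test keeps its level under no effect, and the dilution is toward zero.

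**Conclusion.** The concern holds and should be fixed. Confidence is high that the rule acts after randomization, on one arm, without a working counterpart in the other, and that the plan does nothing to offset it. The magnitude is illustrative: under the assumed removal counts and correlations, a true effect of 0.81 SD would be estimated at 0.60 to 0.75 SD if removed controls aerosolize more, or at 0.87 to 1.02 SD if they aerosolize less. With no removals, or removals unrelated to aerosol, there is no bias. Understated control-arm variability is the lesser effect.

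**What to change.** Leave the decision to place a mask exactly as it is and change what follows for the study:
- Keep the subject in the study and continue particle measurement.
- Define the primary analysis set as all randomized subjects with particle data, analysed by assigned arm.
- State that the facemask-necessity criterion is judged before randomization; otherwise its during-procedure wording re-creates the same removal. Treat any other in-procedure event alike in both arms.
- Record the time of mask placement in controls, and report crossovers and oxygen changes by arm.
- As a supportive sensitivity analysis, show the result without crossed-over controls or, if the download is time-resolved, with their data only up to mask placement. This analysis is itself open to selection.
- Use the 10 spare places only for subjects without particle data, continuing the same randomization sequence.

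The direct cost is protocol wording, an analysis-set definition and one time field. The facemask-criterion change narrows an eligibility rule and should be made openly as such. Analysis up to mask placement needs time-resolved counts. Data Collection specifies only summaries ("Peak and mean aerosolized particle counts. This will be obtained during three intervals for six different sizes"), so the counter's output should be checked first.

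The statistical cost is the dilution. If the crossed-over subjects do not differ, power falls from 0.82 to 0.74 (3/28) or from 0.83 to 0.71 (5/30). If they aerosolize more (r = 0.7), retention gains power: 0.79 against 0.69, or 0.77 against 0.62. The change is needed before enrolment, because data not collected after removal cannot be recovered.

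### Randomisation in the holding area precedes the point at which some open-ended exclusions can be met, and the plan has no rule for patients who meet them after allocation

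*Combined protocol and SAP*

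**What the plan says.** Research Procedure (combined protocol and SAP) places randomisation "at the time of enrollment in the pre-procedure holding area". The sentence before it says that patients having an upper endoscopic procedure in the designated room under monitored anesthesia care "will be eligible for recruitment into the study once exclusion criteria are applied".

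The Exclusion Criteria under Methods include three items with no time limit:

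- "Any patient requiring endotracheal intubation"
- "Patients who require use of a facemask before or during the procedure due to medical necessity"
- "Any procedure done outside the designated procedure room"

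The last item in the same list is expressly a post-randomisation removal from the trial, made on the judgement of the anesthesia physician: "a subject who was randomized to the control arm requires placement of the procedural mask to augment oxygenation, the subject will be removed from the" […].

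Sample Population adds: "An additional 10 patients will be enrolled to account for subject dropout as necessary".

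Data Collection has the 5-minute baseline count taken in the procedure room, before sedation. Sample Size Calculation and Data Analysis makes the baseline one of the three intervals in the primary endpoint. The documents describe no blinding and define no analysis population. They give no rule for following, reporting or replacing a patient who becomes ineligible after allocation.

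**The concern.** Eligibility criteria protect a randomised comparison only if they are settled before allocation. Here a patient can pass every criterion in the holding area, be allocated, and then meet one because the room changes or the airway plan changes. The plan does not say whether that patient stays in the analysis.

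The mask is visible and no blinding is described, so it is a sound inference, though not stated, that the staff making these decisions would know the arm. The documents treat the mask as able to augment oxygenation, so airway-related removals could plausibly be more common in one arm. If those patients also tend to have unusual particle counts, the remaining groups are no longer comparable.

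The baseline raises a separate question. It is recorded after allocation, and the documents do not say when the mask goes on. If it is already on during those 5 minutes, the baseline is not a pre-treatment value.

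**Working it through.** **Order of events.** Enrolment and randomisation (holding area), then room entry, 5-minute baseline, sedation, endoscopy, and 5 minutes of counts after scope removal. Against that order:

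| Criterion | Checkable before allocation | Can still be met after allocation | Arm |
|---|---|---|---|
| Intubation | the plan | conversion | either |
| Medically necessary facemask | need before the procedure | need during the procedure | in practice mainly control |
| Outside the designated room | room booked | change of room | either |
| Control needing the procedural mask | no | yes, expressly | control only |
| Baseline count | – | no exclusion refers to it | – |

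**The plan's own figures.** The target is 50 (25 per arm) plus 10. The allowance is 10/60 = 16.7% of enrolment, consistent with 50/(1 − 1/6) = 60. The 50 itself cannot be reproduced, because no effect size, SD or precision target is given.

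**Bias if removal is selective.** All inputs here are assumptions: 30 randomised per arm, no true mask effect, counts in SD units.

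- Simple case. Removing k of 30 patients who average +1 SD leaves a mean of −k/(30 − k). For k = 5 this is −5/25 = −0.20 SD; for k = 3 it is −3/27 = −0.11 SD.
- Weaker case. The k patients at highest latent risk are removed, and that risk has correlation ρ with the count. The shift is −ρ·φ(a)/(1 − q), with q the share removed and a the standard normal (1 − q) quantile. For k = 5, q = 0.167, a = 0.967 and φ(a) = 0.250, so φ(a)/(1 − q) = 0.300. The shift is −0.09 SD at ρ = 0.3 and −0.15 SD at ρ = 0.5.

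Simulation of the weaker case (20,000 repeats, two-sided t-test at 0.05) gives the spurious mask-minus-control difference in SD, with type I error in brackets:

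| Removed control / mask | ρ = 0 | ρ = 0.3 | ρ = 0.5 |
|---|---|---|---|
| 5 / 0 | 0.00 (0.048) | 0.09 (0.062) | 0.15 (0.086) |
| 7 / 3 | 0.00 (0.050) | 0.06 (0.056) | 0.10 (0.074) |
| 5 / 5 | 0.00 (0.050) | 0.00 (0.047) | 0.00 (0.055) |

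Bias therefore needs both unequal removal and a link with the count. Losing high-count controls would understate a benefit of the mask; losing high-count mask patients would exaggerate it.

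**Cost if removal is unrelated to arm or count.** With 25 per arm, 80% power and a two-sided 0.05 test, the implied standardised difference is (1.960 + 0.842) × √(2/25) = 0.79. With 20 and 25 analysed, SE = √(1/20 + 1/25) = 0.30, and power is Φ(0.792/0.30 − 1.960) = 0.75. There is no bias, only lost precision.

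**The case against.** The strongest reply is that the protocol already puts eligibility first. It applies exclusions before recruitment and makes the designated room and monitored anesthesia care part of eligibility. A reader might infer that the room and airway plan are unsettled at randomisation; the text does not support that. What remains is unplanned later change, of unknown frequency.

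Other tempting inferences also go too far:

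- *That the plan states that patients are removed from both arms.* The only express post-randomisation removal is control-only. Removal after a room change or intubation is a reading of open-ended criteria. It is a natural reading, because the same list already removes a randomised subject, but it is still a reading.
- *That the baseline leads to removals.* No exclusion depends on it. Its timing is a separate matter, and since counts come from an automated counter in a standardised position, knowledge of the arm alone has little route to bias it. The open question is whether the mask is on.
- *That the 10 extra patients are the expected number of such exclusions.* The plan says only that they cover dropout. Consent withdrawal, cancellation, counter failure and the control-arm removal rule could all use that allowance.
- *That 0.20 SD is the expected bias.* It is an assumed one-sided case. Room changes are mainly logistical and would not be expected to produce it.

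It is also fair to say that a cut-off plus analysis by assigned arm gives most of the protection wherever randomisation takes place, and that moving randomisation does not reach conversions after sedation. Both points stand. The fix therefore includes an analysis rule, and the move is justified by fewer avoidable losses and a certain pre-allocation baseline.

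**Conclusion.** The point holds as a gap in the plan and a cheap improvement, not as a demonstrated bias. Randomisation precedes the time at which three exclusions can still be met, those exclusions have no cut-off, and nothing says how allocated patients who meet them are analysed. Arm-related loss is plausible for airway decisions and unlikely for room changes.

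For 5 versus 0 removed, the illustrative size is about 0.1 to 0.2 SD. This rests on 30 per arm, one-sided removal, and an assumed link between removal and count. Equal removal by the same mechanism, or removal unrelated to the count, gives essentially no bias. The baseline question is real but separate: as written, a pre-treatment baseline is not guaranteed.

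**What to change.** 1. Keep consent in the holding area. Open the allocation in the designated procedure room after the room, the monitored anesthesia care plan and the existing exclusions are confirmed and the 5-minute pre-sedation baseline is recorded.
2. State that entry exclusions apply only up to that moment. Consented patients who fail them earlier are screen failures.
3. Add to the analysis section that every randomised patient with particle data stays in the primary analysis by assigned arm, and that any later departure (change of room, intubation, mask use in a control) is reported by arm and reason. Reconcile the last exclusion item with this rule. The change concerns whose data are analysed, not how any patient is managed.

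The first two steps avoid most losses from room changes and airway decisions made before sedation, and ensure that the baseline precedes allocation. Only the third deals with conversions after sedation.

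The cost is a revised sentence in Research Procedure, a clause in the exclusion list and a short analysis-population statement. In practice, the mask must be at hand in the room for every case, and a few consented patients will never be randomised.

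### Brief procedural events carry no clock time and counts are summarised over the whole procedure, so the planned clinical-factor model cannot link an event to the readings around it

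*Combined protocol and SAP*

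**What the plan says.** The Data Collection section, under data collected during the procedure, lists head or neck manipulation, "Any removal and reinsertion of the endoscope", "Any opening of the designated procedure room door" and "Any use of the endoscope working channel". No time, count or duration is asked for with any of them.

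For the counter, the same list specifies "Peak and mean aerosolized particle counts. This will be obtained during three intervals for six different sizes". The second and third intervals are "B. Intra-procedurally and C. Post procedurally for 5 minutes, which is defined as beginning after the endoscope is removed", so the whole procedure, whatever its length, is one interval. Total procedure duration and procedure type are both collected.

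The Sample Size Calculation and Data Analysis section states: "A linear mixed model will be used to assess the association between the clinical factors and concentration level of each particle". The model is there to handle within-subject correlation. The section does not say which factors enter, whether the outcome is the mean or the peak, what the unit of observation is, or whether duration is adjusted for. The primary endpoint, defined in the same section, is a mean or median per interval.

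Of the counter, the Research Procedure section says: "This data can be directly downloaded from the device using the associated Comet software". The sampling interval, and whether the raw series is kept, are not stated.

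**The concern.** A jaw thrust, a reinsertion or a door opening is brief. If it releases or moves particles, the signal lies in the readings around that moment. With no event time and one summary per procedure, the analysis can only compare patients by their event history over the whole procedure.

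Two problems follow. A real burst is averaged with all the quiet minutes, more so in longer procedures. And longer procedures offer more chances for an event, so if counts also differ by length, for example between upper endoscopy and ERCP, an event with no effect can look associated. A door opening may also change the room air, and without times it cannot be separated from a burst coming from the patient.

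At stake is what this pilot can tell the larger trial about sources of variation in aerosol. Event times not written down during the procedure cannot be recovered afterwards.

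**Working it through.** The plan gives no figure for this analysis, so there is none to reproduce. The 50 patients come from the Sample Population section. Event rate, burst size, durations and SDs are not in the documents; every value below is an assumption.

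**1. Dilution.** If an event multiplies the count by r for b minutes of a procedure lasting T minutes, the interval mean rises by (r − 1) × b / T. With r = 2 and b = 1:
- T = 10: 1/10 = 10%
- T = 20: 1/20 = 5%
- T = 45: 1/45 = 2.2%
- T = 60: 1/60 = 1.7%

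**2. Link with length.** With events at random, one per 15 minutes, P(any) = 1 − exp(−T/15).
- T = 10: 1 − exp(−0.667) = 0.487
- T = 45: 1 − exp(−3) = 0.950

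With half the patients at each length, the mean probability is (0.487 + 0.950)/2 = 0.718. The share of variance in having any event that length explains is ((0.950 − 0.487)/2)² / (0.718 × 0.282) = 0.0537/0.2025, or about 27%. With continuous log-normal durations (medians 10 to 30 minutes, one event per 5 to 60 minutes), the share is 5-15%.

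**3. False positives when the event has no effect.** 50 patients, half at 10 and half at 45 minutes, one event per 15 minutes, log-SD 0.5, 4,000 simulated trials, log count compared by any-event status:

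| Assumed excess count in long procedures | Unadjusted p < 0.05 | Adjusted for length |
|---|---|---|
| 0% | 5% | about 5-6% |
| 10% | 6% | about 5% |
| 30% | 15% (runs gave 14.6-15.9%) | about 5-6% |
| 50% | 28% | 5% |

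At 30%, the spurious ratio is about 1.17. With continuous durations (median 20 minutes, residual log-SD 0.8), unadjusted rejection is about 5%, 8%, 15% and 36-38% when log count rises by 0, 0.25, 0.5 and 1.0 per log-unit of duration. Adjusting for log duration returns all of these to 4.5-5.4%.

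**4. Does adjustment recover a real effect?** Same 10/45-minute setting, each event truly doubling the count for 1 minute, 1-minute samples, within-patient log-SD 0.3 or 0.5. The length-adjusted any-event analysis of the interval mean estimates a ratio of about 1.12, with power about 10%. A time-matched analysis of individual samples estimates 2.0, with power near 100%. Allowing for serial correlation and carry-over, the ranges are 1.12-1.30 with 10-25% power, against 1.7-2.0 with power still near 100%.

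**5. Does peak recover it?** In an idealised case where the peak equals the burst level, a doubling shows as about 2.0 by peak, against 1.04-1.24 by mean. But a maximum over more samples is larger by chance. With no event effect and no effect of length on the mean, peak was 22-40% higher in 45-minute procedures, and any-event status reached p < 0.05 in 10-19% of trials.

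**The case against.** The strongest reply is that much is unspecified rather than wrong. The event list is a set of bullets, not a case report form. A reader might infer that events are stored only as yes/no, but the wording can equally mean that every instance is noted. A reader might also infer that the model's outcome is the mean; the plan says only concentration level, and peak is collected too. Both points stand. Neither removes the gap: an untimed list of instances cannot be matched to readings, and a peak without event times could belong to a door opening, a jaw thrust or neither.

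A second tempting inference is that having any event largely stands in for procedure length. The documents do not show this. Length explains about 27% of it even in the extreme 10/45-minute split and 5-15% in milder scenarios. The bias needs counts to depend on length, and the duration and type needed for adjustment are already collected. That disposes of the false positives but not of the dilution in step 4.

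Third, it would go too far to say the trial fails its purpose. Its aims are population variability and the facemask effect, and the randomised comparison does not use the event variables.

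Finally, a sample-level model with only a patient random effect would ignore serial correlation and carry-over; the Introduction itself says droplets may stay suspended for hours. That objection is right and shapes the fix.

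**Conclusion.** The concern holds in limited form. As written, the secondary clinical-factor analysis cannot link head or neck manipulation, scope reinsertion, door opening or working-channel use to the readings around them, however the event list is read. Under the assumed 1-minute doubling, the interval mean moves by only 2.2-10% for procedures of 45 down to 10 minutes, and a true twofold effect is seen as roughly 1.1-1.3 with 10-25% power even after adjustment for length. Confounding with length is partial, conditional on counts varying with length, and removable with data already collected.

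The direction of the dilution follows from averaging; its size rests on the assumed burst, event rate, durations and SDs. The randomised facemask comparison is not affected. The point should be acted on before enrolment, because the missing times cannot be reconstructed.

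**What to change.** - Record the clock time of each listed event, with the recorder's clock set to the counter.
- State that the downloaded sample-by-sample series will be retained.
- For these event factors, fit the mixed model to individual counter samples, with a time-matched event indicator including a short lag for carry-over, a patient random effect, and a serial-correlation structure such as AR(1).
- For any interval-level analysis, name the outcome summary (mean or peak) in advance and adjust for procedure duration and type.

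The cost is a time column, clock synchronisation and somewhat more data handling; no additional patients are needed. Resolution will be limited by the counter's sampling interval, which the plan should state: if samples are long relative to the events, part of the gain is lost.
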